4.5.2 SECONDARY OUTCOME

The Secondary endpoint of the study will be evaluated as the technical performance of CathVision ECGenius® System during routine EP procedures.

- To log time stamp for arrhythmia termination when termination is successful
- To confirm compatibility of CathVision ECGenius® system with commercially available 3D mapping systems and with available intracardiac catheters.
- To have no or minimal device malfunctions reported with the use of the CathVision ECGenius

4.6 STUDY PROCEDURES

The following is a detailed list of study visits and the required procedures/tests. Specific tests/procedures are described in Section 5.

4.6.1 INFORMED CONSENT

Pre-screening, i.e., medical record review without obtaining informed consent, is allowed.

Prior to enrollment of any subjects into the study, written approval of the protocol and informed consent must be obtained from the Institutional Review Board (IRB).

Informed consent will be obtained as outlined in 21 CFR Part 50 and the Good Clinical Practice: Integrated Addendum to ICH E6 (R1) (ICH E6 (R2), 9 November 2016).

A research study member at the IRB approved study site will speak with the study candidate about the purpose of the study and investigational research. Explanation of the study background, study procedures, visits, assessments, risks, and benefits will be reviewed in detail with the potential subject.

The potential subject will be given the time they need to read through the study information and informed consent document and ask as many questions as necessary to make them comfortable with the study and the requirements. After informed consent is obtained, study assessments may begin.

After informed consent is obtained, the study eligibility criteria are checked. All patients who signed a consent form are considered study subjects. A patient is considered enrolled after the patient has signed the informed consent form and after the inclusion/exclusion criteria have been met.

The original informed consent form will be retained with the subject records. A copy of the informed consent will be provided to the subject or legal representative. The informed consent must be written in a language in which the subject or his/her legal representative is fluent. If a foreign language translation is required, a statement of certification of the translation must be issued. Regulations require that foreign language informed consent forms be submitted to the IRB for approval. The investigator must forward a copy of the consent form, the certified foreign language translation, and an IRB approval letter to the Sponsor or its designee.

4.6.2 SUBJECT IDENTIFICATION

To maintain confidentiality, the subject's name will not be recorded on any study document other than the informed consent form. Each enrolled subject will be assigned a study specific Subject Identification Number (SID) will be assigned in consecutive order in the following format: CP00003-SSYYY. CP00003 is the study number, SS is the site number, and YYY is the 3-digit sequential subject ID number starting with 001. For example, the first subject at site 01 will be assigned CP00003-01001. Subject ID numbers will not be re-used (e.g., if the subject is determined to be a screen failure).

4.7 STUDY VISITS

4.7.1 SCHEDULE OF ASSESSMENTS

	Screening	Day 0 Index Procedure
Visit Number	1	2
Informed Consent	✓	
Demographics	✓	
Cardiac History	✓	
Cardiac Anti-Arrhythmia Medications	✓	
Inclusion/Exclusion	✓	
Physical Exam	✓	
Vital Signs	✓	✓
12 lead EKG	✓	
EP procedure		✓
Adverse Events		✓
Device Malfunction		✓

4.7.2 VISIT 1: DAY -15 ± 15 (SCREENING VISIT)

Screening will be completed within 30 days of the index EP and/or ablation procedure. Test results from routinely performed standard assessments may be used to determine eligibility. Initial screening will consist of a review of relevant cardiac history including duration and frequency of arrhythmia(s), their subsequent treatments (e.g., medications, previous ablation), and associated symptoms.

Eligibility will be assessed sequentially, starting with the least invasive and least expensive tests as follows. Results from each test or screening activity should be reviewed prior to proceeding to the next step.

- Demographics
- Baseline cardiac history
- Arrhythmia history (Type of arrhythmia, TTM, EKG, Holter, etc.)
- Baseline cardiac anti-arrhythmia medications
- Physical Examination
- Vital Signs
- 12-lead EKG

Any protocol deviations during screening will be documented per section 8.2.

4.7.3 SCREEN FAILURES

Subjects not meeting all study entry criteria will be designated as screen failures. End of study procedures will not be performed for these subjects, but their reason for ineligibility will be

recorded on the Screening Log. Screen failures after the screening visit are counted towards total study enrollment.

4.7.4 VISIT 2: DAY 0 (INDEX PROCEDURE THROUGH DISCHARGE)

During the index EP procedure, institutional standard of care is to be utilized to treat the subject.

When the subject is connected to the standard EP recording system, during manipulation of catheters or diagnostic tests, intracardiac signals will be recorded using the investigational device in parallel. The total procedure time is not expected to differ by adding the CathVision ECGenius® system to the EP system as the final comparison of data recorded from the Standard EP recording system and the tested device will occur post procedure.

Prior to discharge, the following will be documented:

- Adverse events (AE)
- CathVision ECGenius device malfunctions
- Protocol deviations

Subjects will be considered to have completed and exit the study after this visit.

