4.8 STUDY COMPLETION

4.8.1 COMPLETED SUBJECTS

Subjects will be considered complete when all assessments through the Discharge have been performed in accordance with the protocol. There will be no follow up requirement for this study.

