6.6 DEVICE MALFUNCTIONS

Device deficiency is defined as an inadequacy of a medical device with respect to its identity, quality, durability, reliability, safety, or performance.

Note, device deficiencies include malfunctions and use errors. All device deficiencies that occur during the trial will be recorded.

Device malfunction: failure of an investigational medical device to perform per its intended purpose when used in accordance with the instructions for use.

User error: act or omission of an act that results in a different medical device response than intended by the manufacturer or expected by the user.

The Device Deficiency CRF is specific for reporting all device deficiencies, or malfunctions that occur during the trial, whether or not they were associated with an adverse event. Device Deficiency CRFs should be submitted to the Sponsor within 24 hours of the occurrence defining the device deficiency.

Anticipated device deficiencies and malfunctions with any standard of care EP system include but are not limited to:

- Catheter deflection deficiency or failure
- Malfunction of a catheter electrode
- Malfunction of a catheter temperature sensor
- Unexpected termination of ablation due to internal system error
- Failure to initiate ablation due to internal system error
- Temporary or sustained loss of catheter navigation/visualization capability/signal

Record any CathVision ECGenius® system deficiencies and malfunctions including but are not limited to:

- ECGenius® system issues (Cube® EPAMP/RecSW)
 - Not able to power on
 - Power indicators not on
 - Not able to connect to the standard of care EP system
 - Not able to retrieve signal from standard of care EP system
 - Not able to power down
 - Database issues
 - Backup data issues
 - Not possible to clear fault without reboot
- ECGenius® Recorder Software
 - Malfunction
 - Loss of power
 - Loss of wave form
 - Recording issues (interruption, stop)
 - Not able to create patient
 - Not able to save patient
 - Live Mode issues (not able to create/resume patient, etc)

- Review Mode issues (not able to retrieve a patient)
- SW crashes
- SW loses connection to EPAMP
- Limitation: Only possible to review the latest recording file, while streaming is active
- Bug: Not possible to use the notch filter, if high-pass and low-pass is set to ‘None’
- Host Computer Malfunctions
 - Not able to boot/start
- User errors
 - Not recording data

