7.2 DESCRIPTIVE ANALYSES

Continuous variables will be summarized using standard quantitative statistics: number of available observations, mean, standard deviation, median, quartiles, and range (minimum and maximum observed values). The number of missing observations, if any, will also be summarized.

Categorical variables will be summarized using classical frequency statistics: number of non-missing observations and percentages by categories. Number and percent of missing data, if any, will also be summarized.

There are no predefined criteria for terminating the study based on statistical outcomes. Missing data will not be replaced or imputed.

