## 5.6. Statistical analysis

Endpoint	Statistical method	Hypothesis & benchmark
Freedom from major adverse events, evaluated at hospital discharge.	
 
• Count number of AEs
 
• Percentage: [Procedures with AE] / [Total number of procedures]
 
	
 
• 3.5% of patients develop major AE within 30 days of procedure.
 
• Zero CathVision Cube-related AE are expected.
 

Recording low-voltage electrograms	
 
• Count number of low-voltage electrograms plotted in total
 
• Percentage: [Total number low-voltage electrogram plots] / [Total number of procedures]
 
• Physician user quantitatively score low-voltage electrogram plots on “ease” of interpretation of EGMs” [0-5] on CathVision Cube and on existing EP system 
 
○ 0: Impossible
 
○ 1: Very difficult
 
 
 
	
 
• At least one low-voltage electrogram plot per procedure
 
• CathVision not inferior to existing EP recording system
 

Document no.:	Effective Date:	Version: 1
Author: [name]	Approver:	Reviewer:

Endpoint	Statistical method	Hypothesis & benchmark
	
 
 2: Difficult
 
 3: Possible
 
 4: Easy
 
 5: Very easy
 
 
 
• Average physician score on CathVision ECGenius™ vs average physician score on existing EP system
 
	
Assessing the improved signal quality (baseline noise level peak-to-peak)	
 
• Peak-to-peak amplitude of baseline noise, on unipolar electrogram, at at least 1 site with low-voltage electrograms, and averaged if more than 1.
 
• Peak-to-peak amplitude of baseline noise, on bipolar electrogram, at at least 1 site with low-voltage electrograms, and averaged if more than 1.
 
• Non-inferior peak-to-peak amplitude of baseline noise to existing EP recording system.
 
	
 
• Hypothesis is below 50uV unipolar baseline noise peak-to-peak
 
• Hypothesis is below 20uV bipolar baseline noise peak-to-peak
 
• Hypothesis is non-inferior to existing EP recording system.
 

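### SAP 5.6 has no per-procedure measure of technical success, so a lost ECGenius recording drops out of the score and noise averages instead of counting as a failure

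*Protocol*

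**What the plan says.** **Endpoint.** Protocol 4.5.1 and SAP 5.4 define primary performance as technical success in collecting and recording intracardiac signals. Protocol 4.5.2 adds a secondary endpoint of few or no reported malfunctions, without a numerical threshold.

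**Timing.** The schedule in Protocol 4.7.1 places device malfunction on Day 0 only. Section 4.7.4 says "Prior to discharge, the following will be documented" and lists adverse events, ECGenius malfunctions and protocol deviations. It also says that "the final comparison of data recorded from the Standard EP recording system and the tested device will occur post procedure", with no date, and then "Subjects will be considered to have completed and exit the study after this visit". Section 4.8.1 adds: "There will be no follow up requirement for this study".

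**Deficiency reporting.** Protocol 6.6 requires every device deficiency arising in the trial to be recorded on its own CRF. The listed items include "Review Mode issues (not able to retrieve a patient", database and backup problems, recording interruptions and, under user errors, data not being recorded. On timing: "Device Deficiency CRFs should be submitted to the Sponsor within 24 hours of the occurrence defining the device deficiency".

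**Analysis.** Protocol 7.2 states "Missing data will not be replaced or imputed", and asks for the number of missing observations to be summarised. SAP 5.6 has three relevant measures:
- a low-voltage percentage, which is total plots divided by total procedures, with a benchmark of one or more plots in each procedure;
- "Average physician score on CathVision ECGenius™ vs average physician score on existing EP system";
- peak-to-peak baseline noise at one or more low-voltage sites per procedure, averaged if there are several.

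None of these says what happens to a procedure that yields no ECGenius recording.

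**The concern.** For a recording system, the most direct failure is that no recording results. When that happens there is nothing to score and no noise to measure, so the value is missing because the system, or its operation, failed. An average over the surviving recordings describes quality given that recording worked. The primary endpoint asks whether recording worked.

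The risk of a silent loss is plausible from the protocol's own description. ECGenius records passively and does not direct care (4.2), so nobody depends clinically on its output during the case. Section 6.6 notes that only the latest file can be reviewed while streaming is active. No step requires anyone to open the saved file before the Visit 2 malfunction record is completed.

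At stake is a final report with favourable score and noise averages in which failed recordings appear only as a smaller number of observations.

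**Working it through.** **Inputs.** The planned maximum is 30 subjects (Protocol 4.2, SAP 5.5). The SAP's own basis reproduces: (30 + 20 + 40)/3 = 30. The documents give no loss rate, expected score, standard deviation or non-inferiority margin. The loss counts, the score of 4.0, the score of 0 for a lost recording and the plots per procedure used below are therefore assumptions.

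**Step 1: how each SAP 5.6 measure treats a lost recording.**

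| Measure | Divisor | Effect of a lost recording |
|---|---|---|
| Low-voltage percentage | All procedures | Stays in the divisor, but plots from other cases can offset it |
| Low-voltage benchmark | Each procedure | Fails, if checked case by case |
| Mean physician score | Recordings scored | Drops out |
| Baseline noise | Recordings measured | Drops out |

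**Step 2: physician score.** Let k of 30 recordings be lost and the rest average 4.0. The available-case mean is 4.0 for every k. With each lost recording scored 0, the lowest SAP category, the all-procedure mean is 4.0 × (30 − k)/30:
- k = 1: 4.0 × 29/30 = 3.87
- k = 2: 4.0 × 28/30 = 3.73
- k = 3: 4.0 × 27/30 = 3.60

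Noise has no natural worst value, so the same calculation cannot be made there. The average simply describes the working recordings.

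**Step 3: low-voltage percentage, with k = 3.**
- One plot per retained procedure: 27/30 = 90%, so the loss shows.
- Two plots per retained procedure: 54/30 = 180%, so the loss is hidden although all 30 procedures are in the divisor.

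**Step 4: what a per-procedure proportion would show.** With k = 3, technical failure is 3/30 = 10.0% (exact 95% CI 2.1% to 26.5%). Success is therefore 27/30 = 90.0% (73.5% to 97.9%).

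**Step 5: how likely a loss is.** The chance of at least one loss in 30 is 1 − (1 − p)^30, taking procedures as independent:
- p = 2%: 45.5%
- p = 5%: 78.5%
- p = 10%: 95.8%

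**Step 6: the reporting clock.** Section 6.6 counts 24 hours from occurrence. For a failed retrieval, the occurrence can be read as the failed attempt itself, and the deadline works. If data were never recorded, the occurrence is the procedure. A loss found more than 24 hours later is overdue before anyone knows of it.

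**The case against.** The strongest reply is that malfunction capture does not end at discharge. Section 6.6 covers all deficiencies in the trial, uses an event-driven CRF with no discharge cut-off, and names retrieval, database, backup and non-recording failures. The subject's exit in 4.7.4 ends the subject's participation, not the device record. Source verification (8.7) and close-out (8.8) give further chances to record a loss. All of this stands. A reader might infer that malfunctions found at data review go uncounted, so that the malfunction rate reads 0% despite real losses. The documents do not support that: it would take a breach of 6.6. A late report is still a recorded deficiency.

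Nor does a comparison after the procedure have to follow discharge, since Visit 2 itself runs through discharge. Calling it final does not rule out earlier viewing. The recorder software displays signals to the user (2.1) and trained site staff operate it (3), so some interruptions would be seen live.

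It is also fair to say that losses are not invisible. Section 7.2 reports missing counts, and a procedure without a plot would fail the benchmark if checked individually.

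None of this supplies the missing rule. A missing count does not say why the value is missing, the stated percentage is pooled, and a deficiency log is not an analysis of technical success. That the study is descriptive, with no hypothesis-based sample size (7.1), makes a clear success proportion more useful.

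**Conclusion.** The point holds as a gap in the analysis rules, with a smaller operational gap beside it. Followed as written, SAP 5.6 and Protocol 7.2 give score and noise results restricted to recordings that worked, for an endpoint defined as success in recording. When the system caused the loss, this favours the device.

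The size cannot be taken from the documents. If 1 to 3 of 30 recordings are lost, the technical failure proportion is 3.3% to 10%, and an assumed mean of 4.0 would become 3.87 to 3.60 with losses scored 0. These figures are illustrative. Thirty is also the enrolment ceiling, so with fewer procedures each loss weighs more.

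The operational gap is limited to two items: no check of the saved file before the Visit 2 malfunction record is completed, and a clock that cannot work for a silent failure found late. It does not extend to malfunctions going unrecorded after discharge.

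**What to change.** **SAP 5.6**
- Count as a technical failure any procedure in which ECGenius connection was attempted but no evaluable recording was obtained.
- Over all procedures with connection attempted, report the proportion with an evaluable recording and, separately, the proportion with at least one low-voltage plot.
- Show the score and noise averages beside these proportions, with the number of recordings lost by reason.
- If a worst-score sensitivity analysis is added, first reconcile the scales. Protocol 4.5.1 makes 1 the best score, whereas SAP 5.6 runs from 0 to 5 with 5 the easiest to interpret.

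**Protocol 4.7.4 and 6.6**
- Confirm at the end of the case that the ECGenius file is saved and opens, and record the result.
- State that deficiency recording stays open until the comparison of the two systems is complete.
- Run the 24-hour clock from awareness.

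**Cost.** Wording changes in both documents, one CRF field and a brief file check, with no extra patient visit. The reported success rate may be slightly lower.

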4.8 STUDY COMPLETION

4.8.1 COMPLETED SUBJECTS

Subjects will be considered complete when all assessments through the Discharge have been performed in accordance with the protocol. There will be no follow up requirement for this study.

4.8.2 DISCONTINUED SUBJECTS

Subjects may withdraw consent at any time throughout the course of the trial. The investigator may discontinue a subject from the study at any time if they consider that remaining in the study compromises the subject's health or the subject is not sufficiently cooperative. In either event, reason(s) for discontinuation should be documented appropriately.

Possible reasons for study discontinuation include the following:

- Adverse events (AEs) necessitating discontinuation from the study.
- Subject decision (specify).
- Investigator decision (specify).
- Other reason (specify).

The reasons for any subject discontinuation will be documented on the study completion form of the study Case Report Form (CRF). If possible, subjects who withdraw before study completion will complete the reporting of data as best possible, at minimum AE assessment and CathVision ECGenius® system device malfunction, if applicable.

4.8.3 PREMATURE STUDY TERMINATION

The Sponsor, Investigators, Competent Authority, or Institutional Review Board have the right to suspend or terminate the study prematurely for any safety, ethical, or administrative reason at any time.

The study will be suspended or prematurely terminated if, in the opinion of the Sponsor, Investigator, Competent Authority, or reviewing IRB, the safety of patients and/or data is uncertain. The sponsor should make sure that the suspension or premature termination will be communicated to the Principle Investigator (PI) and reviewing IRB.

CathVision reserves the right to suspend/terminate the investigational site from the study for any of the following reasons:

- Failure to obtain written Informed Consent
- Investigator failure to comply with training or Instructions for Use
- Failure to report SAEs/SADEs/UADEs to Sponsor within 24 hours of knowledge
- Loss of (or unaccounted for) investigational product inventory
- Repeated protocol violations
- Repeated failure to complete case report forms prior to scheduled monitoring visits

The decision to resume study enrollment and treatment at the site will be made by the Sponsor. Additionally, the triggering of the stopping/re-activation will promptly be submitted to the involved Competent Authority and reviewing IRB for approval.

In case of study termination, patients enrolled in the study would be treated and monitored per standard of care and best clinical practices at the investigator's discretion.

4.9 INVESTIGATIONAL DEVICE ACCOUNTABILITY

Documentation of receipt, use, and return of the CathVision ECGenius® System and its parts must be maintained by the Principal Investigator (PI) or his/her designee in a device accountability log. Investigational devices are to be used only in accordance with this protocol and under supervision of the PI or a duly designated person. It is the PI's responsibility to ensure that all study devices are kept in a secure location, with access limited to individuals authorized by the investigator. A record of all study devices (by their lot or serial numbers) received, used, and returned must be maintained by the site until the conclusion of the study. Following accountability of the study devices by the Sponsor or its designee, all study devices will be returned to the Sponsor/Designee as directed in writing by the Sponsor or designee.

5. EXAMINATIONS AND EVALUATIONS

5.1 DEMOGRAPHICS

Date of birth, gender, race, ethnicity, height, and weight will be recorded.

5.2 CARDIAC HISTORY

Relevant cardiac history including duration and frequency of arrhythmia(s), their subsequent treatments (e.g., medications, previous ablation) and associated symptoms will be obtained at Screening. All positive and negative findings will be carefully documented. Any new finding discovered during the Screening evaluation and prior to the index ablation procedure will be considered to be part of the cardiac history and will not be recorded as an AE.

5.3 PHYSICAL EXAM

A physical exam will be performed at Screening. Any abnormalities, if clinically significant, should be recorded.

5.4 12 LEAD EKG

A 12-lead electrocardiogram (EKG) will be conducted. The EKG recording will be printed out and will be placed with subject records. A copy of the EKG recording, and report summary will be made available for the study and filed with the subject study records. Any clinically significant abnormalities will be documented.

